**Table 6 Analysis Populations**

Population	Description
Intent-to-treat	The Intent-to-Treat (ITT) population is defined as all participants who give informed consent, are randomized, and receive at least one dose of study treatment (active or placebo). For the ITT population, data will be analyzed according to the treatment participants were randomized to. The ITT population is the primary population of interest.
Safety	The Safety population is defined as all participants who give informed consent, receive at least one dose of study medication (active or placebo) and will be grouped according to the actual treatment received. The Safety population will be used for the analyses of all safety endpoints.
Efficacy	The ITT population will be used for the analyses of all efficacy endpoints.
Pharmacokinetic	All participants in the safety population who have data from at least one post-dose sample will be included in the PK analysis population. Participants will be excluded from the PK analysis population if they significantly violate the inclusion or exclusion criteria, deviate significantly from the protocol, or if data are unavailable or incomplete which may influence the PK analysis. Excluded cases will be documented together with the reason for exclusion. All decisions on exclusions from the analysis will be made prior to database closure.

## 9.4 STATISTICAL ANALYSES

### 9.4.1 Demographics and Baseline Characteristics

Demographics, baseline characteristics (including subject disposition and medical history) and all baseline laboratory values will be summarized descriptively by treatment using frequency tables and summary statistics providing means, medians, standard deviations, and extreme values.

**Definition of baseline:** Baseline for all efficacy and safety analyses is defined as the last non-missing value recorded prior to or on the first study drug administration.

### 9.4.2 Efficacy Analyses

For the primary and exploratory efficacy analyses, see [Table 7](#).

All efficacy data will be summarized by randomized treatment group and visit for the ITT population.

Participants in whom any of the events (i) to (iii) described in Section 6.5.3 occur in either eye, or participants who require rescue treatment prior to the week 36 assessment will still be considered as completing participants and will enter the analysis as non-responders at the visit at which the event occurs as well as all subsequent visits.

The primary endpoint will be analyzed using GEE with a binomial distribution using a logit link function for odds ratios and unstructured covariance. In case of convergence issues, an alternative covariance structure will be used. The model will include categorical covariates for treatment group, visit, and visit by treatment group interaction term. Also the baseline stratification factors will be added. Least squares means on the probability scale for each treatment group with the corresponding 90% confidence intervals and odds ratios relative to the placebo group will be computed for each visit. Full details of the statistical analysis will be described in a separate document prior to any unmasking of the study.

In accordance with the ITT principle, assessments at all visits will be included in the analysis. This includes any assessments made at visits while the participant is on randomized study treatment as well as any assessments made at visits after randomized study treatment has been terminated.

If visits occur as described in Section 1.3, a response assessment at week 36 will be available for all participants. Despite best efforts, there may be missing response assessments at week 36 (e.g., for participants withdrawing consent or being lost to follow-up). *The statistical methodology to deal with missing data will be described in a separate technical document prior to any unmasking of the study.*

The proposed methodology is known to render unbiased effect estimates only under the restrictive missing completely at random assumption (Liang and Zeger, 1986). Therefore, if the amount of total missing data (across patients and visits) exceeds 10% of all expected data, sensitivity *analyses* will be carried out (Molenbergs and Verbeke, 2005).

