#### **4.2.4 Rationale for Response Definition and Study Eye Selection**

The primary endpoint will be the proportion of participants with a  $\geq 2$ -step improvement from baseline in ETDRS DRSS at 36 weeks, measured in the study eye. At any time, new ASNV, new PDR, new DME and pre-existing DME requiring intervention (see permitted therapies Section [6.5.1](#)), occurring in the study eye will classify a participant as a non-responder for the primary analysis, as all these events imply progression of the disease.

Since RG7774 is an oral treatment with expected bilateral effects, the Sponsor will evaluate an in-patient (sum of both eyes) DRSS improvement of  $\geq 3$  steps in participants with two eligible eyes. At any time, new ASNV, new PDR, new DME and pre-existing DME requiring intervention (see permitted therapies Section 6.5.1), occurring in either eye, classifies a participant as a non-responder. An additional analysis will be conducted for each baseline DRSS level 35 and 43 in the non-study eye to allow for further characterization of RG7774 effects.

In cases where both eyes are eligible, the study eye will be the one with DRSS score of 53. The risk of progression of the disease is higher in eyes with DRSS 53, meaning this population is the one with the higher unmet need (Ip et al. 2015; ETDRS report 1991). If both eyes have the same DR score, then the right eye will be selected as the study eye.

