### **6.5.3 Rescue Medicine and Follow-Up**

If participants during the course of the study were to develop any disease-related events:

- (i) Worsening of DME (when DME present at baseline) requiring treatment at the discretion of the Investigator or if any of the following criteria applies, e.g.:
  - Loss of  $\geq 10$  letters in BCVA as compared to baseline due to DME, or,
  - Loss of  $\geq 5$  letters in BCVA as compared to previous visit due to DME, or,
  - Increase in CST  $\geq 100$   $\mu\text{m}$  as compared to previous visit due to DME.
- (ii) Incident DME or PDR (not present at baseline) requiring treatment.
- (iii) Anterior-Segment Neovascularization (ASNV).

then participants may receive rescue treatment for any eye at the Investigator's discretion with any of the permitted therapies outlined in Section 6.5.1. The date and time of rescue medication administration as well as the name and dosage regimen of the rescue medication must be recorded. Treatment with RG7774 or placebo (as applicable) should continue.

In this situation, a reduced number of assessments will be performed for both eyes if the study eye receives rescue treatment.

If the eye that receives rescue treatment is the non-study eye, the non-study eye will undergo the reduced schedule of assessments, while the study eye will undergo the full schedule of assessments.

This schedule will continue for all remaining visits (until week 36 included; see Section 1.3 and Table 2). This strategy will enable collection of relevant data in participants being treated with the permitted therapies but with a reduced burden for the participants.

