## **9. STATISTICAL CONSIDERATIONS**

### **9.1 STATISTICAL HYPOTHESES**

Denoted by  $p_k$  the proportion of participants with  $\geq 2$  step improvement in ETDRS DRSS from baseline at Week 36 measured in the study eye in treatment group  $k$  ( $k = 0$  for placebo and  $k = 1, 2$ , for low, and high dose, respectively), the hypotheses

$$p_0 = p_k, k = 1, 2,$$

will each be tested at the two-sided 10% level. Due to the exploratory dose finding nature of the study no adjustments for multiplicity will be made. Hypothesis testing will be performed using the framework of Generalized Estimating Equations (GEE), as it takes into account repeated measures within each participant and can provide unbiased effect estimates even if the correlation structure between measures is misspecified.

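### The primary endpoint has two conflicting non-responder rules: study-eye events only (Section 4.2.4) or events in either eye (Section 9.4.2)

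*Combined protocol and SAP*

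**What the plan says.** Section 4.2.4 sets two rules for two analyses. For the primary endpoint, the listed progression events "occurring in the study eye will classify a participant as a non-responder for the primary analysis". The next paragraph covers the 3-step improvement summed over both eyes, where the same events "occurring in either eye, classifies a participant as a non-responder".

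Section 9.4.2 sets one rule. Its first clause covers "Participants in whom any of the events (i) to (iii) described in Section 6.5.3 occur in either eye". A second clause extends the rule to anyone needing rescue before Week 36. Both groups "will enter the analysis as non-responders at the visit at which the event occurs as well as all subsequent visits". The paragraph names no endpoint, and its rescue clause names no eye. The primary GEE model is specified in the next paragraph.

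Two other sections bear on the point. Section 9.1 defines the tested proportion by a "step improvement in ETDRS DRSS from baseline at Week 36 measured in the study eye in treatment group". Section 6.5.3 allows rescue of any eye and states that, when only the fellow eye is rescued, "the non-study eye will undergo the reduced schedule of assessments, while the study eye will undergo the full schedule of assessments".

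**The concern.** The two rules disagree on a case that can arise. Rescue is allowed in either eye, bilateral disease is a randomization stratum, and DME may be present in either eye at entry. Take a participant whose study eye shows a 2-step improvement at Week 36 and whose only event was in the fellow eye. Section 4.2.4 counts a success. Section 9.4.2 counts a failure from the event visit onward, although the study eye was never treated and stayed on the full schedule.

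This is the definition of the endpoint in the trial's only formal hypothesis tests. Two analysts who each follow the protocol could report different primary odds ratios from the same data. If the rule were chosen after treatment codes are known, the choice could be driven by the result. Section 9.5 allows up to two optional unmasked efficacy interims, so that point may come before the final analysis.

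**Working it through.** **Text comparison**

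| | Section 4.2.4 | Section 9.4.2 |
|---|---|---|
| Applies to | Primary analysis, by name | No endpoint named; the primary model follows |
| Eye, for events | Study eye | Either eye |
| Eye, for rescue | Not a separate trigger | None named |
| Either-eye rule | Both-eyes 3-step endpoint only | No such limit |
| Event list | ASNV, new PDR, new DME, pre-existing DME needing intervention | Section 6.5.3 (i) to (iii), plus any need for rescue |

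The event lists also seem to differ. Section 6.5.3(ii) reads "Incident DME or PDR (not present at baseline) requiring treatment", and 6.5.3(i) adds acuity and thickness criteria for DME present at baseline. How large this gap is depends on whether the intervention qualifier in 4.2.4 covers new PDR and new DME or only pre-existing DME.

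**Reproducing the plan's power (Section 9.2)**

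Inputs: 15% placebo, 40% to 45% active, 40 completers per arm, Fisher's exact test, two-sided 0.10. Enumerating all 41 × 41 outcomes gives 75.5% (15% vs 40%) and 87.5% (15% vs 45%), against the stated 74% and 88%. The plan's figures are reproduced to within 2 points.

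**Effect of the either-eye rule**

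Assumptions, none of them taken from the documents: the planning rates are study-eye rates (Section 9.2 does not say), and the either-eye rule reclassifies a share q0 of placebo and qA of active study-eye responders.

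- p0' = 0.15 × (1 − q0)
- pA' = pA × (1 − qA)
- Odds ratio = [pA'/(1 − pA')] / [p0'/(1 − p0')]

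Example with q0 = qA = 0.20 and pA = 0.40: p0' = 0.12 and pA' = 0.32. The odds ratio is (0.32/0.68)/(0.12/0.88) = 3.45.

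| q0 / qA | OR, 15 vs 40 | Difference (points) | Power | OR, 15 vs 45 | Power |
|---|---|---|---|---|---|
| 0 / 0 (study-eye rule) | 3.78 | 25.0 | 75.5% | 4.64 | 87.5% |
| 10% / 10% | 3.60 | 22.5 | 69.4% | 4.36 | 82.4% |
| 20% / 20% | 3.45 | 20.0 | 62.6% | 4.13 | 76.0% |
| 30% / 30% | 3.31 | 17.5 | 54.9% | 3.92 | 68.4% |
| 10% / 5% | 3.93 | 24.5 | 75.7% | 4.78 | 87.2% |
| 20% / 10% | 4.13 | 24.0 | 76.0% | 4.99 | 87.1% |
| 30% / 15% | 4.39 | 23.5 | 76.6% | 5.28 | 87.1% |

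With equal shares, the odds ratio, difference and power all fall. When the active share is half the placebo share, the odds ratio rises above its study-eye value and power barely changes. The difference in proportions falls in every reclassification row. It would rise only if 0.40 × qA < 0.15 × q0, that is, if qA were below 0.375 × q0.

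In head counts, the planning rates give 40 × 0.15 = 6 placebo and 40 × 0.40 = 16 active responders per 40. A 10% share is therefore 0.6 and 1.6 participants.

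**The case against.** The best defence is that the specific rule governs the general one. Only Section 4.2.4 ties a rule by name to the primary analysis, while the 9.4.2 paragraph is generic and precedes any mention of the primary model. That reading is available, but the text does not compel it. The paragraph refers to completing participants, to the Week 36 assessment and to responder status, all of which suggest the primary endpoint.

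Section 9.4.2 also defers full analysis details to a separate document due before unmasking. That document may settle the rule, but it is not in the file. The defect shown is therefore contradictory protocol text, not an analysis known to be uncontrolled.

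Several narrower objections stand:

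- Section 9.1 says where the score is measured, not how intercurrent events are handled, so it supports the study-eye rule without settling the question.
- Any non-responder rule overwrites observed data. After study-eye rescue, fundus photography continues under Table 2, yet 4.2.4 still codes failure.
- The reference in 4.2.4 to Section 6.5.1, which speaks of DME needing treatment, narrows the gap between the event lists.
- For an oral drug expected to act in both eyes, an either-eye composite would be defensible if chosen deliberately.
- The power figures use Fisher's test, as in Section 9.2, whereas the primary analysis is a repeated-measures GEE.
- The study is a proof of concept with unadjusted 10% tests.

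None of these reconciles the two sections.

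**Conclusion.** The concern holds. The protocol gives two incompatible non-responder rules for its primary endpoint and no order of precedence. That conclusion rests on the text alone.

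The numerical effect cannot be determined, because no fellow-eye-only event rate is given. Under the assumed shares for 15% versus 40%, the odds ratio runs from 3.31 to 4.39 around 3.78, and power from 54.9% to 76.6% around 75.5%. The either-eye rule cannot be assumed conservative on the odds-ratio scale, which is the scale of the primary model.

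The mismatch in event lists is secondary. So is a further gap: 9.4.2 does not say how a non-responder is coded for the exploratory worsening endpoints.

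**What to change.** Settle the following before any unmasking, including any optional interim:

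1. In Section 9.4.2, limit both the event clause and the rescue clause to the study eye for the primary and other study-eye responder endpoints, as 4.2.4 already states for the primary analysis.
2. Keep the either-eye rule only for the both-eyes 3-step improvement endpoint. If an either-eye version of the primary endpoint is wanted because the drug is oral, report it as a labelled supplementary analysis.
3. Use a single list of analysis events in 4.2.4 and 9.4.2. This concerns endpoint coding only and leaves the rescue criteria in 6.5.3 untouched.
4. State that being coded a non-responder does not mean being coded as not worsened in the exploratory worsening analyses.

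The separate analysis document should carry the same wording. The cost is a text change: no new participants, visits or data are needed, since study-eye assessments after fellow-eye rescue are already scheduled.

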**Table 3 Objectives and Endpoints**

Objectives	Endpoints
Primary	

 
• Assess the effect of RG7774 on the severity of DR.
 
• Evaluate the safety and tolerability of RG7774.
 
	
 
• Proportion of participants with <math>\geq 2</math> step improvement in the Early Treatment Diabetic Retinopathy Study (ETDRS) DR severity score (DRSS) from baseline at Week 36 measured in the study eye.
 
• Frequency and severity of adverse events.
 

Secondary	

 
• Assess the effect of RG7774 on progression to vision-threatening DR.
 
• Assess the effect of RG7774 on visual acuity.
 
	
 
• Incidence of anterior segment neovascularization (ASNV), new PDR, new DME, and pre-existing DME requiring intervention.
 
• Change from baseline in BCVA at Week 36 in the study eye.
 

Exploratory	

 
• Assess the effect of RG7774 on DR worsening.
 
	
 
• Proportion of participants with <math>\geq 2</math> step worsening in ETDRS DRSS from baseline at Week 36 measured in the study eye
 

 
• Assess the effect of RG7774 on DR severity at a participant level.
 
	
 
• Proportion of participants with <math>\geq 3</math> step improvement in ETDRS DRSS from baseline at post-baseline visits measured in both eyes
 
• Proportion of participants with <math>\geq 3</math> step worsening from baseline at post-baseline visits measured in both eyes.
 

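### Sections 4.2.4 and 9.4.2 use different event lists to set non-response on the primary endpoint, so the same study eye can be classified both ways

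*Combined protocol and SAP*

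**What the plan says.** Section 4.2.4 sets the rule expressly for the primary analysis. It lists "At any time, new ASNV, new PDR, new DME and pre-existing DME requiring intervention", adds a cross-reference to the permitted therapies in Section 6.5.1, and says that these events "occurring in the study eye will classify a participant as a non-responder for the primary analysis". The reason given is progression, not treatment: "as all these events imply progression of the disease".

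The secondary progression endpoint in Table 3 uses the same list: ASNV, "new PDR, new DME, and pre-existing DME requiring intervention". Table 7 repeats it.

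Section 9.4.2 states a different rule. It names "Participants in whom any of the events (i) to (iii) described in Section 6.5.3 occur", in either eye, then adds, as an alternative, participants who require rescue treatment before the Week 36 assessment. Both kinds of participant are non-responders at the event visit and at every later visit.

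The events in Section 6.5.3 were written to govern rescue:

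- Item (i) is worsening of DME present at baseline. It is met if treatment is required in the investigator's judgement, or if one of several criteria applies. These are a loss of at least 10 letters against baseline, a loss of at least 5 "letters in BCVA as compared to previous visit due to DME", or a CST increase of at least 100 µm against the previous visit. Each criterion must be due to DME.
- Item (ii) is "Incident DME or PDR (not present at baseline) requiring treatment".
- Item (iii) is ASNV, without a qualifier.

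Once an event has occurred, rescue is optional.

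**The concern.** Both sections define non-response on the only primary efficacy endpoint, and they do not name the same events. No sentence gives one precedence. Responder status for some participants would therefore depend on which section the programmer follows.

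Section 9.4.2 leaves full analysis details to a separate document, to be written before unmasking. That document is not among those supplied, and it would inherit two conflicting sources. Section 9.5 also allows up to two efficacy interim analyses by unmasked staff, so the choice could come to be made, or appear to be made, with results in view.

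Under 9.4.2 the primary endpoint would also use a different event list from the secondary progression endpoint. That is not an error in itself, but it conflicts with the rationale given in 4.2.4.

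**Working it through.** **Step 1: the two rules side by side.** Take events in the study eye up to Week 36, with no event in the other eye, so that only the event list differs.

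| Event | 4.2.4 | 9.4.2 via 6.5.3 |
|---|---|---|
| ASNV | counts | counts, item (iii) |
| New PDR, treatment required | counts | counts, item (ii) |
| New PDR, treatment not required | counts | does not count |
| New DME, treatment required | counts | counts, item (ii) |
| New DME, treatment not required | counts | does not count |
| Pre-existing DME, intervention required | counts | counts, item (i) |
| Pre-existing DME, item (i) criterion met due to DME, no intervention required | does not count | counts |

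Three rows differ.

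**Step 2: which differences can change the endpoint.** The PDR row has little practical effect. Entry requires DRSS 47 or 53, both non-proliferative. An eye that has PDR at Week 36 has moved up the scale, so it cannot show a 2-step improvement and fails on DRSS alone. Two cases remain, each with at least 2 steps of improvement at Week 36:

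- Case A: no DME at baseline, new DME at Week 24 that does not require treatment. Non-responder under 4.2.4, responder under 9.4.2.
- Case B: DME at baseline, a 6.5.3(i) criterion met due to DME, no intervention judged necessary. Responder under 4.2.4, non-responder under 9.4.2 from that visit on.

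The cases move the count in opposite directions. Case B needs DME at baseline. Section 4.2.1 caps participants with DME at 50%, so at the planned size at most 0.5 × 135 = 67.5, that is 67, could be exposed to it. That is a ceiling on exposure, not a rate of discordance.

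**Step 3: scale, by assumption only.** The plan gives no figure for reclassification, so its power figure serves as reference. Inputs from Section 9.2: 15% response on placebo, 40% to 45% on active, 40 completers per group, Fisher's exact test, two-sided 0.10. Power is the sum of Bin(a; 40, p0) × Bin(b; 40, p1) over all outcomes (a, b) with Fisher p ≤ 0.10.

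- Computed: 75.5% (15% vs 40%) and 87.5% (15% vs 45%), against 74% and 88% stated. Reproduced within 2 points.
- Sample size: 40 / (1 − 0.10) = 44.4, rounded up to 45; 3 × 45 = 135. Reproduced.

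Now suppose that a share f of would-be responders in every arm becomes non-responders, so each rate is multiplied by (1 − f). For f = 10% the rates are 13.5% against 36% or 40.5%.

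| f (assumed) | 15% vs 40% | 15% vs 45% |
|---|---|---|
| 0 | 75.5% | 87.5% |
| 5% | 72.5% | 85.1% |
| 10% | 69.4% | 82.4% |
| 20% | 62.6% | 76.0% |

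This shows sensitivity to an equal loss in all arms. It does not estimate what either rule would do.

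**The case against.** The strongest reply is that the sections can be read as one rule.

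- The qualifier about intervention in 4.2.4 could cover its whole list, because the cross-reference leads to Section 6.5.1, where incident DME appears as DME requiring treatment. That would remove Case A.
- The criteria in 6.5.3(i) are introduced as examples and could be read as describing when treatment is required. That would remove Case B.

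Both readings are possible, and both are needed to remove the conflict. Both are also less literal. In Table 3 and Table 7 a comma separates pre-existing DME requiring intervention from new DME, and the progression rationale does not depend on treatment. Section 6.5.3(i) joins investigator judgement and the criteria with an or, and 9.4.2 lists the events and the need for rescue as alternatives, so an event counts without rescue.

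Three stronger readings are tempting, and the documents do not support them.

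- A reader might infer that ordinary acuity test variation would erase many DRSS responses under the 5-letter criterion. Each criterion must be due to DME, so a fluctuation from measurement noise does not meet it.
- A reader might take the 41% one-year progression in Section 4.2.1 as the size of the problem. It is overall progression to vision-threatening disease, much of which would count under both rules.
- A reader might infer from the open time wording in 4.2.4 that events in Weeks 36 to 48 reach back to the endpoint. The endpoint is response at Week 36, and 9.4.2 starts non-response at the event visit, so a later event cannot change it.

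The trial is also a hypothesis-generating proof of concept. That lowers the stakes, but it does not settle which participants are responders.

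**Conclusion.** The conflict is real on the literal text. Two sections give different event lists for the same primary-analysis rule, and Cases A and B come out oppositely. The conclusion rests on two readings: that the intervention qualifier in 4.2.4 belongs to pre-existing DME only, and that a 6.5.3(i) criterion can be met without intervention being required.

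The size is unknown. The documents give no rate for untreated new DME in improved eyes, nor for criterion-only worsening of baseline DME. Section 4.2.1 does report that treatment was deferred for at least a year in most patients, even those with DME, so Case A is not contrived, but that gives no rate for this trial. A reader might infer that 9.4.2 dilutes the contrast between active and placebo. No such direction follows, because the two cases work against each other and their balance by arm is unknown.

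It should still be corrected before unmasking, because the primary endpoint must have one definition and wording alone provides it.

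**What to change.** Before any unmasking, including an optional interim analysis under Section 9.5, reconcile Sections 4.2.4 and 9.4.2 into one event list for the primary analysis.

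The list already stated for that analysis in 4.2.4, and matched in Table 3, fits the stated progression rationale: ASNV, new PDR, new DME, and pre-existing DME requiring intervention, with the window given as up to and including Week 36.

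Rewrite the whole 9.4.2 sentence, not only its cross-reference:

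- cite that list in place of 6.5.3 (i) to (iii);
- state whether meeting a 6.5.3(i) BCVA or CST criterion without intervention counts as non-response;
- resolve either eye against study eye, noting that 4.2.4 uses the study eye for the primary analysis and either eye for the two-eye analysis;
- state how the rescue clause fits, and who determines that intervention was required.

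Carry the same text into the separate analysis document. Leave the rescue rules in 6.5.3 unchanged; the edit concerns endpoint classification only.

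The cost is wording. The secondary endpoint already requires these events to be counted, so no new data are needed. The number of non-responders may shift in either direction.
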